Data will be analysed using appropriate statistical software (eg STATA, SPSS). Continuous variables will be assessed for normality, and non-normally distributed variables will be transformed as appropriate or will be assessed using non-parametric tests if appropriate. The data and samples collected will enable both cross-sectional and longitudinal analyses, and thus to define the prevalence and incidence of clinical outcomes of interest respectively. We will quantify the relationship between the clinical outcomes of interest, and potential underlying exposures (lifestyle, environmental, genetic) risk factors using regression techniques. For the assessment of relationship between a continuous primary and secondary outcome we will carry out mixed models analysis of covariance (e.g., BP, HbA1c, blood cholesterol, serum creatinine) etc. Mixed models logistic regression will be used to assess the association between explanatory and categorical outcome variables (e.g., T2D, CVD, hypertension, hypercholesterolemia). Statistical significance will be inferred at P<0.05, using techniques (eg Bonferroni) to control for multiple comparisons where appropriate. Where complementary phenotypic or molecular information is available from the preciously completed LOLIPOP study, we will carry out joint analysis of the LOLIPOP and LOLIPOP 100K datasets.

The LOLIPOP 100K study provide high statistical power for identifying environmental and genetic factors as well as their interaction effect that contribute to incidence of diabetes and cardiovascular disease, and the outcomes for these diseases in UK South Asians compared to Europeans. Based on the disease incidence observed amongst the current South Asian participants of the LOLIPOP study, we estimate that 10 year follow-up of 100K South Asians will yield >10,000 deaths and cases of common diseases such as CHD and T2D, >5,000 cancer cases, including ~2,500 cases of breast cancer, and ~300 cases of uncommon

Imperial College London

endpoints such as end stage renal failure. This affords >80% power to detect an odds ratio of as 1.1 (common diseases) to 1.5 (uncommon diseases) for exposures with prevalence 20%, at P<0.05 (Table). Data and all appropriate documentation will be stored for a minimum of 10 years after the completion of the study, including the follow-up period.

13. Expected value of results

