The Chief Investigator will obtain approval from a recognised NRES Research Ethics Committee & Health Research Authority (HRA) or the corresponding bodies within the devolved participating nations. The study will be submitted for assessment of capacity and capability at each participating NHS Trust using the HRA/REC approved study document set and Organisation Information Document (OID) & Schedule of Events (SoE). The Chief investigator or designee will prepare the documents submission to participating sites and utilise the specified e-mail templates as per the national recommended process. The Chief Investigator will require a copy of each participating site's confirmation of capacity and capability, agreed OID, PI & research teams current CV and GCP certificates, before accepting participants into the study. This information will be stored in the Main Study file located at the research team's offices at Ealing Hospital. The study will be conducted in accordance with the UK Policy Framework for Health & Social Care research . For any Non-NHS sites, a Site-Specific Assessment Form (SSI) will need to be submitted for REC review. The study will be conducted in accordance with the recommendations for physicians involved in research on human subjects adopted by the 18th World Medical Assembly, Helsinki 1964 and later revisions.

27. Indemnity

Imperial College London holds negligent harm and non-negligent harm insurance policies which apply to this study

28. Sponsor

Imperial College London will act as the main Sponsor for this study. Delegated responsibilities will be assigned to the NHS trusts taking part in this study.

Table. Power calculations for the proposed LOLIPOP 100K study. Table summarises i. the incidence of major disease endpoints in South Asians, based on the previously completed LOLIOP study (per 100,000 participants, per year), and ii. the expected number of disease cases that would occur after 10 years in the LOLIPOP 100K study of 100,000 participants. Relative risks detectable are then provided for each of the diseases in a nested case control study (2 controls per case, 90% power), under 3 experimental designs: i. single marker study (P<0.05), ii. Metabolome wide association study (MWAS, P<10⁻⁵) and iii. Genome-wide association study (GWAS, P<5x10⁻⁸). Power is calculated based on an exposure present in 20% of the population, or minor allele frequency 20% for genetic association.

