Disease	Incidence	Expected cases	Single marker study	MWAS	GWAS
Death (all cause)	612	12240	1.08	1.16	1.14
Type 2 diabetes	950	19000	1.06	1.13	1.11
Cardiovascular disease Cancer (all cause)	864 625	17280 12500	1.06 1.06 1.08	1.13	1.11
Myocardial infarction	453	9060	1.09	1.19	1.16
Stroke	221	4420	1.14	1.19	1.24
Breast cancer (F)	251	2510	1.19	1.39	1.32
Prostate cancer (M)	158	1580	1.23	1.51	1.42
Colo-rectal cancer	47	940	1.31	1.69	1.56
Pancreatic cancer	22	440	1.47	2.12	1.89
Stomach cancer	18	360	1.52	2.28	2.01
End stage renal failure	15	300	1.59	2.45	2.14

References

1. Collaboration NCDRF. Worldwide trends in diabetes since 1980: a pooled analysis of 751 population-based studies with 4.4 million participants. Lancet. 2016;387(10027):1513-30.

2. collaborators NCDC. NCD Countdown 2030: worldwide trends in non-communicable disease mortality and progress towards Sustainable Development Goal target 3.4. Lancet. 2018;392(10152):1072-88.

3. Collaboration NCDRF. Worldwide trends in diabetes since 1980: a pooled analysis of 751 population-based studies with 4.4 million participants. Lancet. 2016;387(10027):1513-30.

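### The power table's ten non-sex-specific case counts are twice what its stated 10 years in 100,000 participants can give, and the MWAS and GWAS detectable risks rest on those counts

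*Protocol*

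**What the plan says.** The caption of the power table at the end of the protocol says that incidence is "based on the previously completed LOLIOP study (per 100,000 participants, per year"), and that the next column is "the expected number of disease cases that would occur after 10 years in the LOLIPOP 100K study of 100,000 participants". Detectable relative risks are then given for a "nested case control study (2 controls per case, 90% power"), at three significance levels: "single marker study (P<0.05"), "Metabolome wide association study (MWAS, P<10⁻⁵") and "Genome-wide association study (GWAS, P<5x10⁻⁸"). Exposure prevalence, or minor allele frequency, is 20%.

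The first row reads "Death (all cause) 612 12240".

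Section 12 (Statistical considerations) uses the same horizon: "we estimate that 10 year follow-up of 100K South Asians will yield >10,000 deaths and cases of common diseases such as CHD and T2D". It adds more than 5,000 cancers, about 2,500 breast cancers and about 300 cases of uncommon endpoints such as ESRF. From these it claims more than 80% power at odds ratios from 1.1 (common diseases) to 1.5 (uncommon diseases), with P<0.05.

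Section 6 (Design) plans at least 20 years of follow-up after the last recruitment.

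**The concern.** With the rate per 100,000 per year and 100,000 people watched for 10 years, the expected count is ten times the rate. The table shows twenty times the rate in every row that is not sex-specific. The excess is exactly two throughout, so rounding does not explain it.

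This table and the Section 12 paragraph that cites it are the protocol's only quantitative justification of its size. A reader will take the counts as what the resource can deliver at 10 years, and the relative risks as what can be detected then. The rare endpoints have most to lose, because there the number of cases limits what can be studied.

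**Working it through.** **1. Case counts.** Expected cases = (incidence / 100,000) × 100,000 × 10 = incidence × 10.

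| Endpoint | Incidence | Table | Table ÷ incidence | 10-year count |
|---|---|---|---|---|
| Death | 612 | 12,240 | 20 | 6,120 |
| Type 2 diabetes | 950 | 19,000 | 20 | 9,500 |
| Cardiovascular disease | 864 | 17,280 | 20 | 8,640 |
| All cancer | 625 | 12,500 | 20 | 6,250 |
| Myocardial infarction | 453 | 9,060 | 20 | 4,530 |
| Stroke | 221 | 4,420 | 20 | 2,210 |
| Colorectal cancer | 47 | 940 | 20 | 470 |
| Pancreatic cancer | 22 | 440 | 20 | 220 |
| Stomach cancer | 18 | 360 | 20 | 180 |
| ESRF | 15 | 300 | 20 | 150 |
| Breast cancer (F) | 251 | 2,510 | 10 | 1,255 or 2,510 |
| Prostate cancer (M) | 158 | 1,580 | 10 | 790 or 1,580 |

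For the last two rows, the lower figure assumes rates per 100,000 of one sex and 50,000 people of each sex; the higher takes the caption literally. One rule reproduces all 12 rows: 20 years, with half the cohort for a sex-specific cancer.

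**2. Method for the detectable risks.** Two-proportion test, n cases and 2n controls, p0 = 0.20, p1 = 0.2·OR / (0.8 + 0.2·OR), p̄ = (p1 + 2·p0)/3, two-sided α (the protocol does not state sidedness):

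power = Φ[ (p1 − p0 − z·s0) / s1 ], with s0² = p̄(1 − p̄)·1.5/n and s1² = p1(1 − p1)/n + p0(1 − p0)/(2n).

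For GWAS, alleles are counted, so n becomes 2n.

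**3. Reproducing the table, then halving the counts (90% power).**

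| Endpoint | Stated MWAS/GWAS | Recomputed, tabled counts | Recomputed, 10-year counts |
|---|---|---|---|
| Death | 1.16/1.14 | 1.166/1.137 | 1.24/1.20 |
| Colorectal cancer | 1.69/1.56 | 1.690/1.557 | 2.06/1.84 |
| ESRF | 2.45/2.14 | 2.436/2.124 | 3.40/2.82 |
| Breast cancer | 1.39/1.32 | 1.391/1.320 | 1.58/1.47 (one-sex reading) |

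The tabled counts reproduce these two columns, so the detectable risks rest on them. The stroke MWAS entry (1.19) is an exception: its own inputs give about 1.29.

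**4. Single-marker column.** At the tabled counts this column matches 80% power, not the captioned 90%. For death, 80% gives 1.080 and 90% gives 1.093 (stated 1.08). For ESRF they give 1.587 and 1.701 (stated 1.59). The effect of halving is therefore shown at 80% first:

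| Endpoint | Stated | 10-year count, 80% | 10-year count, 90% |
|---|---|---|---|
| Death | 1.08 | 1.11 | 1.13 |
| Type 2 diabetes | 1.06 | 1.09 | 1.11 |
| ESRF | 1.59 | 1.89 | 2.08 |

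**5. Section 12's power sentence, on 10-year counts, P<0.05.**

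- OR 1.1: type 2 diabetes 87%, cardiovascular disease 84%, all cancer 71%, deaths 70%, myocardial infarction 57%.
- OR 1.5: colorectal 86%, pancreatic 56%, stomach 48%, ESRF 42%.

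Worked case, ESRF with n = 150 and OR 1.5: p1 = 0.3/1.1 = 0.2727; p̄ = 0.2242; s0 = 0.0417; s1 = 0.0431; (0.0727 − 1.96 × 0.0417)/0.0431 = −0.21; power 42%.

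On the tabled counts at OR 1.5, stomach cancer (360 cases) has 76% and ESRF (300 cases) has 69%, so both miss 80% even before halving.

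**The case against.** Four stronger readings are tempting, and the documents do not support them.

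- *Every count is doubled.* This is certain for ten of the 12 rows. With the caption's unit read literally, the breast and prostate counts are right for 10 years. Calling them doubled needs a one-sex denominator and an even split, neither of which the protocol states. The literal reading does not clear the table, however: it would then mix two horizons.
- *All of Section 12's yields are inflated.* Only the 300 ESRF cases are clearly so. More than 5,000 cancers agrees with the 10-year figure of 6,250. The figure of more than 10,000 deaths and common diseases can be read as a combined total, which 10-year counts exceed. The 2,500 breast cancers depend on the denominator.
- *No 10-year power claim is met.* Section 12's claim survives halving for type 2 diabetes and cardiovascular disease at 1.1, and for colorectal cancer at 1.5. Nor is doubling the only cause of the failures, since stomach cancer and ESRF miss at 1.5 on either count.
- *The table was built on 20 years.* This is likely, given the follow-up planned in Section 6, but not proven: 10 years in 200,000 people gives the same counts.

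It can also fairly be said that this is an observational resource with long follow-up planned. If 20 years was meant, the remedy is a change of label, and neither design nor sample size is affected. That limits the consequence, but the stated figures still contradict their own caption.

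**Conclusion.** Wrong as written. Ten of 12 expected-case figures are exactly twice what the caption's rate, horizon and cohort size give, and Section 12 repeats one of them (ESRF, 300 against 150) without ambiguity. The MWAS and GWAS columns inherit the error, apart from the anomalous stroke MWAS entry. The shift is modest for common endpoints and large for rare ones. The single-marker column inherits it too, but also departs from the captioned power, and that is a separate defect.

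The count error needs only the table's own figures. The detectable risks assume a two-sided two-proportion test, with allele counting for GWAS; this closely reproduces the stated MWAS and GWAS entries checked above. The breast and prostate corrections (1,255 and 790) hold only under the one-sex, 50:50 assumption. Simple multiplication ignores attrition and depletion of those at risk, so real 10-year counts would be somewhat lower still.

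**What to change.** Choose one horizon and make the table and Section 12 agree:

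- **Relabel** the table and the Section 12 yields as 20-year figures, which fits the planned follow-up; or
- **Keep 10 years**, halve the ten non-sex-specific counts (and the other two if their rates are per 100,000 of one sex), recompute all three columns, and restate the Section 12 yields, including about 150 ESRF cases.

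Showing both horizons side by side would serve readers best. In either case, state the denominator of the breast and prostate rates, compute all three columns at one stated power, correct the stroke MWAS entry, and rewrite the Section 12 power sentence so that it names the endpoints for which it holds.

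The cost is a protocol wording change and a re-run of the table. The stated figures become less favourable or the stated horizon longer. No extra participants are needed.

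### The stroke entry for the metabolome-wide design (1.19) does not fit its own row: with 4,420 cases the detectable relative risk is about 1.29, and power at 1.19 is about 31%

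*Protocol*

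**What the plan says.** The legend to the power table at the end of the Protocol sets one design for all entries: a "nested case control study (2 controls per case, 90% power"). It adds that "Power is calculated based on an exposure present in 20% of the population", with a 20% minor allele frequency for the genetic column. The threshold for the middle column is given as "Metabolome wide association study (MWAS, P<10⁻⁵"). The other two columns use P<0.05 (single marker) and P<5×10⁻⁸ (GWAS).

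Three rows matter here. In each, the numbers are incidence, expected cases, and the detectable effect for single marker, MWAS and GWAS, in that order:

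- "Myocardial infarction 453 9060 1.09 1.19 1.16"
- "Stroke 221 4420 1.14 1.19 1.24"
- "Breast cancer (F) 251 2510 1.19 1.39 1.32"

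**The concern.** With threshold, power, control ratio and exposure prevalence all held fixed, the detectable effect within a column depends only on the number of cases, and it must grow as cases fall. From myocardial infarction to stroke the cases drop from 9,060 to 4,420. The single-marker value rises from 1.09 to 1.14 and the GWAS value from 1.16 to 1.24, as they should. The MWAS value stays at 1.19. It then jumps to 1.39 for breast cancer with 2,510 cases.

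Stroke is also the only complete row in which the MWAS value is smaller than the GWAS value. In all the others it is larger, for example 1.19 against 1.16 for myocardial infarction and 1.39 against 1.32 for breast cancer.

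Section 3 lists stroke among the cardiovascular sub-phenotypes for which the earlier cohort was too small, and Section 8 plans metabolomic profiling of the stored samples. Anyone sizing a nested metabolomic study of stroke from this cell would expect 90% power for an effect that the design would usually miss.

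**Working it through.** **Inputs.** From the table legend: control exposure p0 = 0.20, 2 controls per case, 90% power, threshold 10⁻⁵. From the stroke row: n = 4,420 cases, hence 8,840 controls. The legend does not say whether the test is one- or two-sided. Two-sided is assumed, so z = 4.417.

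**Formula.** For odds ratio OR, exposure in cases is p1 = 0.2·OR / (0.8 + 0.2·OR). With p̄ = (p1 + 2·p0)/3,

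- SE under the null: s0 = √[p̄(1−p̄)(1/n + 1/2n)]
- SE under the alternative: s1 = √[p1(1−p1)/n + p0(1−p0)/2n]
- Power = Φ[(p1 − p0 − 4.417·s0)/s1]

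The detectable effect is the OR at which power is 0.90. The legend speaks of relative risks. The odds ratio is used because it is the scale on which the other rows reproduce.

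**Reproducing the rest of the MWAS column.**

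| Endpoint | Cases | Stated | Computed |
|---|---|---|---|
| Type 2 diabetes | 19,000 | 1.13 | 1.132 |
| Cardiovascular disease* | 17,280 | 1.13 | 1.139 |
| Death | 12,240 | 1.16 | 1.166 |
| Myocardial infarction | 9,060 | 1.19 | 1.195 |
| **Stroke** | **4,420** | **1.19** | **1.286** |
| Breast cancer | 2,510 | 1.39 | 1.391 |
| Prostate cancer | 1,580 | 1.51 | 1.508 |
| Colorectal cancer | 940 | 1.69 | 1.690 |
| Pancreatic cancer | 440 | 2.12 | 2.109 |
| Stomach cancer | 360 | 2.28 | 2.267 |
| End-stage renal failure | 300 | 2.45 | 2.436 |

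*This row runs together with all-cause cancer in the text at hand. The single legible MWAS value is attributed to cardiovascular disease.

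Ten rows agree to within about 0.015, and their power at the stated value is 83% to 91%. Stroke misses by 1.286 − 1.19 = 0.096.

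**Power at the stated stroke value.** OR = 1.19 gives p1 = 0.238/1.038 = 0.2293, p̄ = 0.2098, s0 = 0.00750, s1 = 0.00762. Then (0.0293 − 4.417 × 0.00750)/0.00762 = −0.50, and power is 31% (0.307; a simulation also gave 0.307). About 9,480 cases would be needed for 90%.

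**Power at the corrected value.** OR = 1.29 gives p1 = 0.2439, s0 = 0.00756, s1 = 0.00773. The argument of Φ is 1.35, and power is 91%.

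**Hand check from the neighbouring rows.** The detectable log odds ratio scales roughly as 1/√cases.

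- From myocardial infarction: ln 1.19 × √(9,060/4,420) = 0.174 × 1.432 = 0.249, so OR ≈ 1.28.
- From breast cancer: ln 1.39 × √(2,510/4,420) = 0.329 × 0.754 = 0.248, so OR ≈ 1.28.

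**Other readings of the legend, for stroke.**

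| Variant | Detectable effect | Power at 1.19 |
|---|---|---|
| Unpooled variance | 1.292 | – |
| Log-odds-ratio test | 1.285 | – |
| One-sided test | 1.278 | 36% |
| 80% power | 1.262 | 31% |
| Direct prevalence ratio | 1.217 | 73% |
| Two alleles counted per person, 10⁻⁵ | 1.197 | 86% |

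Only the last comes near 1.19. It is the genetic set-up, and it fails the rest of the column (breast cancer 1.267 against a stated 1.39). The prevalence-ratio scale fails it too (breast cancer 1.29). The stroke GWAS entry does reproduce with allele counts at 5×10⁻⁸ (1.235 against 1.24), so this discrepancy lies in the MWAS cell and not in the stroke case count used for the row.

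**Dependence on the case count.** The listed 4,420 is 20 times 221, although the legend speaks of 10 years in 100,000 people, which gives 221 × 10 = 2,210. On 2,210 cases the detectable OR is 1.42 and power at 1.19 is 5%. If only the 80,000 South Asians expected in Section 6 contribute, 0.8 × 2,210 = 1,768 cases give 1.48 and 3%.

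**The case against.** The strongest objection is that the protocol may not be wrong at all. The printed 1.19 and the expected 1.29 differ by one digit, the text was read from PDF by a program, and the cardiovascular and cancer rows just above are visibly damaged. If the source table prints 1.29, the point disappears. This cannot be fully excluded. Against it, the stroke row is complete, with all five values in order, and its case count and GWAS value are consistent with each other. The match with the myocardial infarction value above it would also fit a copying slip, but that is inference.

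Second, little hangs on the cell. The power statement in Section 12 concerns odds ratios of 1.1 to 1.5 at P<0.05, and no sample size, endpoint or analysis rule is tied to the MWAS stroke figure. That stands, and it limits how much the error matters. It does not make the figure right.

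Third, the 5% and 3% power figures and the values 1.42 and 1.48 come from a separate discrepancy in the case counts. That is fair: they are conditional on that correction, and the 1,768 figure further assumes that strokes among European participants are not counted. The core result, 1.29 and 31%, needs neither.

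**Conclusion.** The concern holds. On the legend's own terms the stroke MWAS entry should be about 1.29 for 4,420 cases, and the stated 1.19 carries about 31% power instead of 90%. This rests on a two-sided test and the odds-ratio scale. Both are choices that the other ten legible MWAS entries support, and no alternative tried gives 1.19 for stroke while also fitting those entries. It rests as well on the extracted digit being what the source prints, so confidence is moderate. The effect is confined to one planning figure, for an endpoint the Protocol uses to justify the larger cohort. No study procedure changes.

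**What to change.** First check the cell against the source table. If it reads 1.19 there, replace it by 1.29 on the current count of 4,420 cases. If the expected cases are brought into line with the stated 10 years, recalculate the whole column. The stroke entry then becomes 1.42 on 2,210 cases, or 1.48 on 1,768 if only the 80,000 South Asians are counted. The legend should say which population and follow-up period the counts refer to. The cost is one table cell, or one recalculated table if the case counts change as well.
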